6.21. Safety

Safety assessments will consist of evaluating AEs, SAEs and concomitant medications/therapies used to treat them. Safety assessments may include monitoring of any or all of the following parameters: subject's clinical symptoms, physical examination findings, laboratory assessment of hematology and serum chemistry parameters, vital signs, performance status, ECG, echocardiogram, urinalysis, or pregnancy testing for FCCBP/FCBP, pathological, radiological or surgical findings, or other appropriate tests and procedures.

6.21.1. Adverse Events Reporting

All AEs will be recorded by the Investigator from the time the informed consent/assent signing until 28 days after the last dose of lenalidomide, as well as those SAEs made known to the Investigator at any time thereafter that are suspected of being related to lenalidomide. Adverse events, including second malignancies and cardiovascular events, will be monitored and reported throughout the reporting period as AEs/SAEs as applicable. Adverse events and SAEs will be recorded on the AE page of the CRF and in the subject's source documents. All SAEs must be reported to Celgene Drug Safety within 24 hours of the Investigator's knowledge of the event by facsimile, or other appropriate method, using the SAE Report Form, or approved equivalent form. For additional details see Section 11.

6.21.2. Second Primary Malignancies

Second primary malignancies (SPMs) will be monitored as events of interest and should be included as part of the assessment of AEs throughout the course of the study. Investigators are to report any SPM as SAEs regardless of causal relationship to lenalidomide, occurring at any time for the duration of the study, from the time of signing the ICF/IAF until all subjects have been followed for up to 5 years from the last subject's first dose, unless consent is withdrawn, the subject is lost to follow-up or dies. Events of SPM are to be reported using the SAE report form and must be considered an "Important Medical Event" even if no other serious criteria apply; these events must also be documented in the appropriate page(s) of the CRF and subject's source documents. Documentation on the diagnosis of the SPM must be provided at the time of reporting as a SAE (eg, any confirmatory histology or cytology results, X-rays, computed tomography [CT] scans, etc.).

Information about common side effects already known about lenalidomide will be included in the subject informed consent form and should be discussed with the subject as needed during the study. This information can also be found in the Investigator's Brochure (IB) or will be communicated between IB updates in the form of Investigator notifications.

6.22. Treatment Discontinuation

All discontinued subjects, regardless of reason for discontinuation, should undergo treatment discontinuation procedures at the time of IP discontinuation. The treatment discontinuation procedures include physical examination, vital signs, echocardiogram, performance status, hematology, serum blood chemistry, pregnancy testing for FCCBP/FCBP, lenalidomide counseling, collections of AEs, concomitant medications and procedures, IP administration recording, and IP accountability. Bone marrow aspirate/biopsy, peripheral blood smear, cytogenetic testing, and IWG response assessment will be measured. If clinically inappropriate per the treating site, the subject may have bone marrow evaluation omitted if peripheral blast results are collected. The reason for discontinuation will also be documented in the CRF and in the source document.

6.23. Follow-up Phase

Subjects will enter the Follow-up Phase at the time of permanent discontinuation of IP and will be followed for up to 5 years from the last subject's first dose, unless the subject dies, withdraws consent or is lost to follow-up. The Follow-up Phase may not be terminated because of new anticancer treatment or HSCT.

A 28-day Follow-up Visit will occur 28 days after the subject's last dose of IP. At this visit, subjects will be monitored for the collection of AEs and concomitant medications/procedures used to treat the AEs, physical examination (including vital signs), hematology, serum blood chemistry, lenalidomide counseling, SPMs, and anticancer therapies. Female Children of Childbearing Potential and FCBP will have a pregnancy test at the 28-day Follow-up Visit (see Section 6.8 and Section 7.2).

After the 28-day Follow-up Visit, subjects will be followed-up long term by phone or clinic visit, whichever is the institution's normal standard of care, every 3 months for a maximum of 5 years from the last subject's first dose, regardless of new anticancer treatment or HSCT, for SPMs, safety issues (any drug-related SAEs), start of new anticancer therapies, and transition to HSCT.

6.24. Optional Extension Phase

Upon completion of 12 cycles of lenalidomide therapy per protocol, subjects who are demonstrating clinical benefit as assessed by the Investigator and who do not meet any of the criteria for treatment discontinuation (see Section 12) may enter the optional extension phase (OEP). Details for OEP are provided in Appendix L.

6.25. Investigational Product Specific Safety Concerns To Be Monitored or Assessed

Embryo-Fetal Exposure and Pregnancy Warning: Lenalidomide is a chemical analog of thalidomide structurally related to thalidomide. Thalidomide is a known human teratogen that causes severe life-threatening birth defects. Lenalidomide induced malformations in monkeys similar to those described with thalidomide. If lenalidomide is taken during pregnancy, a teratogenic effect of lenalidomide in humans cannot be ruled out. Sexually mature subjects will be required to adhere to the Celgene approved pregnancy prevention program. Additionally, all

subjects and/or parents/guardians will be required to have an understanding that lenalidomide could have a potential teratogenic risk. All FCCBP/FCBP and male subjects will be counseled about pregnancy precautions and risks of fetal exposure according to the REVLIMID REMS (Risk Evaluation and Mitigation Strategies) program ([Lenalidomide IB](#)).

Adverse Events of Specific Concern: Adverse events of specific concerns associated with the administration of lenalidomide observed in adults in marketed indications include:

- *Hematologic toxicity:* Lenalidomide is associated with significant neutropenia and thrombocytopenia. Subjects may require dose interruption and/or dose reduction.
- *Deep vein thrombosis and pulmonary embolism:* Physicians and subjects should be observant for signs and symptoms of thromboembolism. Subjects with a history of non-catheter associated thromboembolic events or with a known genetic predisposition to thrombophilia (ie, Factor V Leiden mutation) will receive prophylactic anticoagulation with low-molecular-weight heparin (LMWH), or other appropriate medication. All other subjects enrolled on study will be considered for prophylactic antithrombotic treatment in accordance with local treatment practices, current treatment guidelines, treating physician discretion, and a careful risk-benefit assessment. Should prophylactic anticoagulation be instituted, the platelet count will be maintained greater than 50,000 with platelets transfusions as needed. If the platelet count cannot be maintained > 50,000 with transfusions, the Investigator should interrupt anticoagulation.
- *Allergic reactions:* Allergic reactions associated with lenalidomide include hypersensitivity, angioedema, Stevens-Johnson syndrome, and toxic epidermal necrolysis (TEN). In some cases, these allergic reactions may be fatal. Lenalidomide will be discontinued if any such reactions are suspected. Lenalidomide will not be resumed following discontinuation for these reactions.
- *Hepatotoxicity:* Hepatic failure, include fatal cases, has occurred in patients treated with lenalidomide in combination with dexamethasone. The mechanism of drug-induced hepatotoxicity is unknown. Pre-existing viral liver disease, elevated baseline liver enzymes, and concomitant medications may be risk factors. Monitor liver enzymes periodically. Stop lenalidomide upon elevation of significantly elevated liver enzymes. After return to baseline values, treatment at a lower dose may be considered.
- *Lenalidomide capsules contain lactose.* The risk-benefit of lenalidomide treatment will be evaluated in subjects with lactose intolerance.
- *Tumor lysis syndrome (TLS):* Fatal instances of TLS have been reported during treatment with lenalidomide. Subjects at risk for TLS (ie, those with high tumor burden) will be closely monitored for development of TLS with the initiation of lenalidomide.
- *Tumor flare reaction (TFR):* Serious tumor flare reactions have occurred during investigational use of lenalidomide for CLL and lymphoma. Although TFR has not been reported in adult AML, patients at risk of TLS (ie, those with high tumor burden) will be closely monitored for development of TFR.

- *Increased mortality due to cardiac events*: Serious and fatal cardiac adverse reactions were observed in patients with CLL. Please refer to the REVLIMID US prescribing information ([REVLIMID USPI](#)) for further information. Appropriate monitoring measures for cardiac toxicity are implemented in the protocol.
- *Second primary malignancy (SPM)*: Higher incidences of SPM were observed in controlled trials of patients with MM receiving lenalidomide. All subjects will be followed for SPM for 5 years from the last subject's first dose of IP, until withdrawal of consent, lost to follow-up or death.
- *Graft-versus-host disease (GVHD)*: GVHD was observed in adult IIT trials investigating lenalidomide as maintenance therapy in patients following allogeneic HSCT in remission ([Kneppers, 2011](#); [Sockel, 2011](#)), and in relapsed MM and relapsed AML patients previously treated with allogeneic HSCT who responded to lenalidomide ([Ades, 2010](#); [Bensinger, 2012](#); [El-Cheikh, 2012](#); [Ford, 2010](#); [Lioznov, 2010](#); [Montefusco, 2012](#)). Additionally, GVHD rash has been reported in relapsed adult AML/MDS and MM patients after achieving CR with lenalidomide post allogeneic stem cell transplantation HSCT ([Blum, 2010](#); [Ford, 2010](#)). Subjects in this study will be closely monitored for GVHD and specific GVHD stopping criteria have been developed. For additional details see Section 8.2.1.

6.26. Pharmacokinetic Sample Collection

6.26.1. Blood Collection for PK Analysis

Collection of blood samples for PK assessments in plasma will be performed in all subjects. On Cycle 1 Day 1, the subjects will receive the dose of lenalidomide in the morning at the study center. Subjects will undergo PK sampling of blood at scheduled time points ([Table 3](#)) for 24 hours postdose. The actual date and time for dosing and blood sampling should be recorded in CRF.

As food may affect the absorption of lenalidomide, subjects will be asked to fast at least 2 hours prior to dosing and 2 hours after dosing of lenalidomide on Day 1 in order to reduce variability in PK results. Approximately 1 mL of blood will be drawn for each PK sample. Specific details regarding the collection, handling, processing, storage, and shipment of PK samples (blood) can be found in [Appendix H](#).

Table 3: PK Sampling Schedule During Cycle 1 Day 1

Collection time after lenalidomide administration ^a	Collection window	Weight ≤ 20 kg ^b	Weight > 20 kg ^c
0.5 hour	± 10 min	-	x
1 hour	± 10 min	x	x
2 hours	± 10 min	x	x
4 hours	± 10 min	x	x
6 hours	± 10 min	-	x
8 hours	± 10 min	x	x
24 hours*	± 2 hours	x	x

PK = pharmacokinetic.

* The 24 hour blood sample must be taken prior to the lenalidomide administration on Day 2.

[figure not shown]
^a The blood draw volume is 1 mL per sample.

^b Only 5 PK blood samples will be taken from subjects with weight ≤ 20 kg at the specified time points.

^c Seven PK blood samples will be taken from subjects with weight > 20 kg.

Subjects should return to the clinic on Day 2 for the 24-hour postdose PK sample, which should be taken prior to lenalidomide administration. However, at the discretion of the Investigator and for convenience of the subject, the subject can be hospitalized overnight at the clinic from Day 1 to Day 2 of Cycle 1 to facilitate collection of the 24-hour postdose sample.

CELGENE PROPRIETARY INFORMATION

7. STUDY POPULATION

7.1. Number of Subjects and Sites

The study will enroll pediatric subjects from 1 to ≤ 18 years of age at the time of screening with rrAML with at least 2 prior induction therapy attempts. A total of up to 43 evaluable subjects (18 in Stage 1 and an additional 25 in Stage 2) are required for assessment of the primary endpoint. To allow for subjects found to be unevaluable for the primary endpoint due to an incorrect diagnosis, not having a disease assessment post screening, or who discontinued prior to receiving lenalidomide, up to 4 additional subjects may be enrolled for a maximum of 47 evaluable subjects across approximately 70 sites. Approximately 50% of enrolled subjects will be younger than 12 years of age to provide adequate PK data for this age subset. The study will be conducted initially in North America (United States of America and Canada) and may be expanded globally.

7.2. Inclusion Criteria

Subjects must satisfy the following criteria to be enrolled in the study:

1. Male or female is 1 to ≤ 18 years of age at the time of signing the ICF/IAF.
2. Subject (when applicable, parental/legal representative) must understand and voluntarily provide permission to the ICF/IAF prior to conducting any study-related assessments/procedures.
3. Subject has rrAML after at least 2 prior induction attempts:
 - Bone marrow aspirate or biopsy must have $\geq 5\%$ blasts by morphology and/or flow cytometry.
 - Each block of chemotherapy (ie, ADE, MA) is a separate reinduction attempt.
 - Donor lymphocyte infusion (DLI) is considered a reinduction attempt.
4. Subject is willing and able to adhere to the study visit schedule and other protocol requirements.
5. Subject has a Karnofsky score of $\geq 50\%$ (subjects ≥ 16 years of age) or a Lansky score $\geq 50\%$ (subjects < 16 years of age).
6. Subject has a resting left ventricular ejection fraction (LVEF) of $\geq 40\%$ obtained by echocardiography.
7. Subject has recovered from the acute toxic effects of all prior chemotherapy, immunotherapy, or radiotherapy prior to first dose. All prior treatment-related toxicities must have resolved to \leq Grade 2 prior to enrollment.
8. Regarding radiation therapy, time elapsed prior to first dose of lenalidomide:
 - 2 weeks for local palliative radiation therapy (XRT).
 - 8 weeks if prior craniospinal chemoradiation therapy (CRT) or if $\geq 50\%$ radiation of pelvis.
 - 6 weeks if other bone marrow radiation has been administered.

9. Graft-versus-host disease criteria:

- Subject must be at least 2 months (from first dose of lenalidomide) from stem cell infusion.
- Subject must have no evidence of active acute or chronic GVHD (Grade 0) for 4 weeks prior to the first dose of lenalidomide.
 - If the subject has a history of maximum Grade 1 or 2 GVHD that was treated with systemic steroid (≥ 0.5 mg/kg/day prednisone equivalents) or other non-steroid systemic IST, the subject must be off all IST for at least 2 weeks, and must have ceased treatment doses of steroids for GVHD (≥ 0.5 mg/kg/day prednisone equivalents) for at least 4 weeks.
 - If the subject has a history of Grade 3 or greater GVHD, the subject must be off all systemic IST for 4 weeks.
 - Topical therapy is permitted and does not imply the subject has active acute or chronic GVHD.
- Physiologic dosing of hydrocortisone is permitted.

10. At least 4 weeks (from first dose) elapsed from donor lymphocyte infusion (DLI) without conditioning.

11. Subject has adequate renal function, which is defined as:

- Creatinine clearance calculated (Table 4) using the Schwartz formula, (Schwartz, 1976) or radioisotope glomerular filtration rate (GFR) > 70 mL/min/1.73 m².

Table 4: Creatinine Clearance Estimation using the Schwartz Formula

Age	Maximum Serum Creatinine (mg/dL)	
	Male	Female
1 month to < 6 months	0.4	0.4
6 months to < 1 year	0.5	0.5
1 to < 2 years	0.6	0.6
2 to < 6 years	0.8	0.8
6 to < 10 years	1.0	1.0
10 to < 13 years	1.2	1.2
13 to < 16 years	1.5	1.4
≥ 16 years	1.7	1.4

The threshold creatinine values in this table were derived from the Schwartz formula for estimating glomerular filtration rate (GFR) (Schwartz, 1976) utilizing child length and stature data published by the Center for Disease Control (CDC).

12. Subject has adequate liver function, which is defined as:

- Total bilirubin is ≤ 2 mg/dL unless the increase in bilirubin is attributable to Gilbert's Syndrome

- AST is ≤ 3.0 x upper normal limit (ULN) for age. For the purpose of this study, the ULN for AST is 50 U/L.
- ALT is ≤ 3.0 x upper normal limit (ULN) for age. For the purpose of this study, the ULN for ALT is 45 U/L.

13. Female Children of Childbearing Potential, Female of Childbearing Potential and male subjects that have reached puberty must agree to undergo physician-approved reproductive education and discuss the side effects of the study therapy on reproduction with parent(s) and/or guardian(s).
14. All subjects and/or parents/guardians must have an understanding that lenalidomide could have a potential teratogenic risk. Female Children of Childbearing Potential, defined as females who have achieved menarche and/or breast development in Tanner Stage 2 or greater and have not undergone a hysterectomy or bilateral oophorectomy and FCCBP defined as a sexually mature woman who has not undergone a hysterectomy or bilateral oophorectomy and has not been naturally postmenopausal for at least 24 consecutive months (ie, has had menses at any time in the preceding 24 consecutive months) must meet the following conditions below (Note: Amenorrhea following cancer therapy does not rule out childbearing potential):

- Medically supervised serum pregnancy tests with a sensitivity of at least 25 mIU/mL must be conducted in FCCBP/FCBP, including those who commit to complete abstinence*. FCCBP/FCBP must have two pregnancy tests (with a minimum sensitivity of 25 mIU/mL) prior to starting treatment with lenalidomide. The first pregnancy test must be performed within 10 – 14 days prior to the start of lenalidomide treatment and the second pregnancy test must be performed within 24 hours prior to starting treatment with lenalidomide.

NOTE: The pregnancy test 10 to 14 days prior to initiation of lenalidomide may be omitted, at the discretion of the investigator, for any FCCBP/FCBP who has high acuity disease requiring immediate treatment with lenalidomide. The pregnancy test within 24 hours prior to the first dose of lenalidomide is required to be performed.

The subject may not receive IP until the Investigator has verified that the results of these pregnancy tests performed on Cycle 1 Day 1 are negative. FCCBP/FCBP with regular or no menstrual cycles must agree to have pregnancy tests weekly for the first 28 days of study participation and then every 28 days while on study, at study Treatment Discontinuation Visit, and at Day 28 following IP discontinuation. If menstrual cycles are irregular, the pregnancy testing must occur weekly for the first 28 days and then every 14 days while on study, at study Treatment Discontinuation Visit, and at Days 14 and 28 following IP discontinuation.

- Female subjects must, as appropriate to age and at the discretion of the study Investigator, either commit to true abstinence* from heterosexual contact (which must be reviewed on a monthly basis) and/or agree to the use of two reliable forms of approved and effective contraceptive methods simultaneously. The two methods of reliable contraception must include one highly effective method and one additional effective (barrier) method (oral, injectable, or implantable hormonal contraceptive; tubal ligation; intra-uterine device; barrier contraceptive with spermicide; or

vasectomized partner) without interruption, 28 days prior to starting lenalidomide treatment, throughout the entire duration of study treatment including dose interruptions and 28 days after the end of study treatment.

- All male and female subjects must follow all requirements defined in the Pregnancy Prevention Program.

15. Male subjects, as appropriate to age and the discretion of the study physician:

- Must practice true abstinence* or agree to use a condom during sexual contact with a pregnant female or a female of childbearing potential while participating in the study, during dose interruptions and for at least 28 days following lenalidomide discontinuation, even if he has undergone a successful vasectomy or practices complete abstinence.

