The primary objective of this study is to determine the activity of lenalidomide in pediatric patients with relapsed/refractory AML (with second or greater relapse or refractory to at least 2 prior induction attempts). Treatment of an AML recurrence following allogeneic HSCT commonly includes a rapid taper of immune-suppression used for prophylaxis and/or treatment of acute GVHD. In this setting, mild GVHD is an expected and a desirable toxicity. The use of the immune-modulatory drug, lenalidomide, in patients at risk for acute GVHD will be challenging but with the potential for benefit to the patient with induction of mild but manageable GVHD. Accordingly, this study will attempt to keep patients with new mild GVHD on protocol therapy, while recognizing that Grade 3 or greater acute GVHD will be an unacceptable toxicity. First, patients with active GVHD or requiring immune-suppression including steroids for GVHD control are not eligible for enrollment. Patients with a history of Grade 3 or greater GVHD or those on therapeutic dosing of immune suppressive therapy will be discussed with the study chair prior to enrollment and require a longer observation time off immune-suppression prior to enrollment (4 weeks) compared to those without a history of severe GVHD or who are already on tapering dosing of immune suppressive therapy without signs of GVHD (2 weeks off immune-suppression) (see Sections 6.25, 7.2 and 8.2.1). Second, patients who develop Grade 3 or greater GVHD, or lower grade GVHD that does not respond to protocol prescribed interventions (Section 8.2.1) will be off study treatment. No dose reduction is planned as it is not clear that this toxicity would improve and be altered by dose adjustment. Incidence of GVHD will be closely monitored and the study will be closed to post-HSCT patients if stopping thresholds for Grade 3 or greater GVHD are crossed (see Section 10.9.1). Patients will be monitored for development of chronic GVHD.

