An external DMC will evaluate safety and treatment activity data in an ongoing and periodic manner to assess benefit-to-risk considerations throughout the study. The function of the DMC is to monitor the safety and activity of the study treatment. Once 4 subjects having received at least one dose of lenalidomide have completed at least 1 cycle of study treatment or discontinued treatment (whichever occurs first), the DMC will evaluate the safety data available and provide a recommendation. The DMC will also provide recommendations about the continuation of the study from Stage 1 to Stage 2 (continue as planned, continue with modifications or stop treatment and/or enrollment) and advise on ways to improve quality. The underlying principles for the DMC are ethical and safety aspects for the subjects. It will be the task of the DMC to examine whether the conduct of the study is still ethically justifiable, whether security of the subjects is ensured, and whether the process of the study is acceptable. For this, the DMC has to be informed about the adherence to the protocol, the subject accrual, and any observed AE(s). The composition and responsibilities of the DMC, including the structure and procedures of its meetings, will be outlined in a DMC charter.

The study consists of 3 phases: Screening Phase, Treatment Phase and Follow-up Phase.

Screening Phase

The Screening Phase will start from the time of signing the informed consent form (ICF)/informed assent form (IAF) and will last no more than 14 days, at which time the Treatment Phase will begin (Cycle 1 Day 1). Subject's screening procedures are to occur during the Screening Phase within 14 days prior to dosing on Cycle 1 Day 1.

As part of the screening procedures, a fresh bone marrow aspirate and/or a bone marrow biopsy paraffin embedded slide will be collected from all subjects for confirmation of disease. The confirmation of disease will be performed locally.

A standard cytogenetic metaphase preparation from the fresh BMA must be prepared for the cytogenetic testing/chromosome analysis including karyotype. The local site will submit the reports of the karyotype, FISH studies, as well as any available data on molecular mutations (FLT3, CEPBa, NPM1, and others including exome sequencing via Foundation Medicine or other sources) if performed, to the central reviewer at [REDACTED]. If subjects have a FISH detectable marker, the test should be repeated until CR/CRi and at relapse.

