7.3. Exclusion Criteria

The presence of any of the following will exclude a subject from enrollment:

1. Subject has Down syndrome.
2. Subject has French-American-British classification (FAB) type M3 leukemia (acute promyelocytic leukemia) or identification of t(15;17).
3. Subject has isolated CNS involvement or extramedullary relapse. (Subjects with combined CNS/marrow relapse may be enrolled).
4. Subject has had prior treatment with cytotoxic chemotherapy within 2 weeks of the first dose of lenalidomide with the exception of hydroxyurea (allowed prior to the first dose of lenalidomide and through Day 14 of Cycle 1) and intrathecal (IT) cytarabine will be administered within 2 weeks prior to administration of lenalidomide.
5. Subject has had prior treatment with biologic antineoplastic agents less than 7 days before the first dose of lenalidomide. For agents that have known AEs occurring beyond 7 days after administration (ie, monoclonal antibodies), this period must be extended beyond the time during which acute AEs are known to occur.
6. Subject has had prior treatment with lenalidomide.
7. Subject is pregnant or lactating.
8. Subject has an uncontrolled systemic fungal, bacterial, or viral infection (defined as ongoing signs/symptoms related to the infection without improvement despite appropriate antibiotics, antiviral therapy, and/or other treatment).
9. Subject has known Human Immunodeficiency Virus (HIV) positivity (subjects who are receiving antiretroviral therapy for HIV disease).
10. Subject has a prior history of malignancies other than AML unless the subject has been free of the disease for ≥ 5 years from first dose of lenalidomide.
11. The presence of any of the following will exclude a subject from enrollment:
 - Subject has any significant medical condition, laboratory abnormality, or psychiatric illness that would prevent the subject from participating in the study.

- Subject has any condition including the presence of laboratory abnormalities, which places the subject at unacceptable risk if he/she were to participate in the study.
 - Subject has any condition that confounds the ability to interpret data from the study.
12. Subject has cardiac disorders (Common Terminology Criteria for Adverse Events [CTCAE] version 4.03 Grade 3 or 4).
 13. Subject has a history of well-documented prior veno-occlusive disease (VOD).

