 - If residual leukemia is demonstrated, which is stable from prior assessments (ie, subject with previous PR/treatment failure), the subject will proceed to the next cycle of lenalidomide as scheduled without delay and without regard to peripheral blood counts. Lenalidomide dose will NOT be decreased.

Special Instructions for Management of Graft Versus Host Disease (GVHD):

Post-HSCT subjects will be monitored closely for development of GVHD of the skin, liver, or gut, see [Appendix K](#) for grading criteria.

- Subjects with Grade 1 or 2 GVHD (any site, biopsy proven or probable, ie, requires systemic steroid treatment) will be managed at the discretion of the local bone marrow transplant (BMT) physician and lenalidomide will be held.
 - If the acute GVHD resolves within 14 days and the subject is being treated with no more than topical therapies and/or up to 0.5 mg/kg/day corticosteroids (prednisone equivalents), lenalidomide will be restarted at the same prior dose.
 - After 14 days, subjects requiring more than 0.5 mg/kg/day corticosteroids or other systemic therapy (ie, not including topical therapies) to manage the acute GVHD will be discontinued from the study.
- Subjects with Grade 3 or 4 GVHD (any site, suspected or biopsy proven) will have lenalidomide discontinued permanently and will be managed at the discretion of the local HSCT physician. These subjects will be discontinued from the study.

Guidelines for Renal Insufficiency

- Lenalidomide is primarily excreted unchanged by the kidney; therefore, study treatment will be held for subjects who experience CLcr < 70 mL/min (confirmed by repeat creatinine measurement within 3 days). If CLcr returns to levels that meet initial eligibility criteria (> 70 mL/min) within 7 days of IP interruption, the subject may resume treatment at a full dose. However, if the subject improves within 14 days, a dose reduction by 1 dose level of study treatment will be considered at the discretion of the Investigator, and after careful consideration of the subject's renal impairment etiology and the subject's tolerability to lenalidomide. If toxicity does not resolve to eligibility by 14 days of dose interruption, then the subject will be off study treatment.

Dose Discontinuation:

- Subjects experiencing a thromboembolic event unrelated to a central line will be discontinued from lenalidomide treatment.

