8.3. Method of Treatment Assignment

All subjects will be enrolled into the study using an IWRS. The Investigator or designated site staff will be assigned password protected, coded identification numbers that give them authorization to log into the IWRS. At screening, the Investigator or designated staff will log into the IWRS and provide the requested identifying information for the subject. The IWRS will then confirm the assignment of a 2-part unique subject number. The first part is the center number and the second part is one of a series of numbers allocated to subjects at that center. Once assigned to a subject, the subject number will not be reused. If the subject is not enrolled into the study the IWRS must be notified.

Prior to enrolling a subject, written ICF/IAF must be obtained, all screening evaluations must be completed, and eligibility criteria must be verified by the Sponsor. Once these actions have been completed, the Investigator or designated staff will log into the IWRS and confirm that the subject fulfills all the inclusion and exclusion criteria. The IWRS will assign an enrollment number to the subject which will be used to identify the subject in the study.

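### Protocol 1.4.2 describes a 2-week immunosuppression washout that criterion 9 of 7.2 does not impose on post-transplant children with no GVHD history

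*Protocol*

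**What the plan says.** Protocol 1.4.2 sets out two intervals off immunosuppression before enrollment. Patients with prior Grade 3 or worse GVHD, or on therapeutic doses of immunosuppression, need 4 weeks, and each such case "will be discussed with the study chair prior to enrollment". The shorter interval is for patients with no history of severe GVHD, or those "already on tapering dosing of immune suppressive therapy without signs of GVHD (2 weeks off immune-suppression) (see Sections 6.25, 7.2 and 8.2.1". The same paragraph says that treating relapse after allogeneic transplant commonly includes "a rapid taper of immune-suppression used for prophylaxis and/or treatment of acute GVHD".

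The entry rule is criterion 9 of 7.2. It requires at least 2 months since stem cell infusion and no active GVHD for 4 weeks. It then gives two washouts, each tied to past GVHD. The first begins "If the subject has a history of maximum Grade 1 or 2 GVHD that was treated with systemic steroid", at 0.5 mg/kg/day prednisone equivalent or more, or with a non-steroid systemic agent. It asks for 2 weeks off all immunosuppression and 4 weeks off treatment-dose steroid. The second asks for 4 weeks off after Grade 3 or worse GVHD. Topical therapy and physiologic hydrocortisone are allowed.

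Section 8.3 makes these criteria the gate to enrollment: "eligibility criteria must be verified by the Sponsor".

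**The concern.** Section 1.4.2 presents the 2 weeks as an entry safeguard and names 7.2 among the sections that implement it. Criterion 9 has no clause for a transplanted child who never had GVHD. Sites and the sponsor check eligibility against 7.2, so the rule that operates is the looser one, and it admits children whom 1.4.2 would hold back. By the protocol's own account of tapering at relapse, children still coming off prophylaxis are to be expected.

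What is at stake is subject protection and clean attribution. If a taper overlaps the first lenalidomide doses, GVHD that follows is harder to assign to either cause. Rates of acute and chronic GVHD are a secondary endpoint (3.2), and Grade 3 or 4 cases count toward the rule that closes post-transplant enrollment (10.9.2).

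**Working it through.** This is a comparison of texts. Table 2 places enrollment on Cycle 1 Day 1, so time before enrollment (1.4.2) and time before first dose (7.2) end on the same day.

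**Step 1. Time off systemic immunosuppression, by GVHD history**

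| Post-transplant child | 1.4.2 | 7.2, criterion 9 |
|---|---|---|
| Prior Grade 3 or worse | 4 weeks | 4 weeks |
| Prior Grade 1–2, treated systemically at or above the threshold (not now on therapeutic doses) | 2 weeks | 2 weeks, plus 4 weeks off treatment-dose steroid |
| Prior Grade 1–2, treated only topically or with steroid below 0.5 mg/kg/day | 2 weeks | none stated |
| No GVHD history | 2 weeks | none stated |

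The gap in the last row is 14 − 0 = 14 days. The third row has the same literal gap. It matters only if the child is also taking something systemic, because topical therapy is expressly allowed.

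**Step 2. Does another section supply the rule?**

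- 6.25 covers monitoring for GVHD and sets no entry washout.
- 7.3, exclusion 11, covers any condition "which places the subject at unacceptable risk if he/she were to participate in the study" or that confounds interpretation. It is a judgement, and it mentions neither immunosuppression nor an interval.
- 8.2.1 manages GVHD arising on study. If it resolves within 14 days and the child is "treated with no more than topical therapies and/or up to 0.5 mg/kg/day corticosteroids (prednisone equivalents), lenalidomide will be restarted at the same prior dose". This suggests that low-dose steroid alongside lenalidomide is tolerated, but it is not an entry rule.
- 9.1 permits supportive care generally. 9.2 prohibits other chemotherapy, live vaccines, biological therapies and other investigational agents, but not immunosuppressants as a class.

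None closes the gap. The study-chair step in 1.4.2 does not appear in 7.2 either.

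**Step 3. Delay if the 2 weeks is enforced**

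Let *t* be the days of taper remaining at consent and *S* the days screening would take anyway. Screening "will last no more than 14 days, at which time the Treatment Phase will begin (Cycle 1 Day 1"), so *S* runs from 0 to 14. The earliest start moves from day *S* to day max(*S*, *t* + 14). Since *t* + 14 is never less than *S*, the added delay is *t* + 14 − *S*.

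- Last dose on the day of consent (*t* = 0): 0 to 14 days, and the washout fits inside screening.
- Still tapering (*t* > 0): the wait from consent is *t* + 14, which exceeds 14 days. Section 6.1 then requires a new consent or assent form for rescreening, and repeat of procedures more than 14 days old.

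**Step 4. The GVHD stopping rule, for context**

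For 4 or more events in 15, the exact binomial probability is 0.0556 at a true rate of 10% and 0.909 at 40%. This agrees with the stated alpha of 0.10 and power of 90%. The calculation uses only 15, 4 and the assumed rate, so the wording of criterion 9 does not enter it.

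**The case against.** The strongest reply is that 1.4.2 is background and 7.2 governs. Criterion 9 is carefully tiered, with a steroid threshold and named allowances, and the amendment summary records that the GVHD entry criteria were clarified. On that view 7.2 is the considered rule and 1.4.2 a loose paraphrase. This stands as a reason not to presume which text should give way. It does not remove the conflict, because 1.4.2 states entry conditions and cites 7.2 for them, and no section says that prophylaxis is allowed at entry.

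A second reply is that patients without severe GVHD history could mean only those with milder past GVHD, which would match criterion 9. The words also fit a child who never had GVHD, and the clause on tapering without signs of GVHD points the same way. Still, that sentence does not name prophylaxis, so the 14-day figure rests on the ordinary reading. Section 1.4.2 also bars patients who need immunosuppression for GVHD control. That could be stretched to cover prophylaxis, but the bar is not in 7.2.

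Third, other protections limit the consequence: the 2 months from infusion, 4 weeks free of GVHD, holding or stopping lenalidomide for GVHD on study, the stopping rule and the data monitoring committee. They do, but none sets a washout. Delay also matters in this disease. The protocol itself waives the earlier pregnancy test when the disease needs immediate treatment.

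Three stronger readings are tempting and unsupported. A reader might infer that the gap raises GVHD or alters response; the documents give no rates by immunosuppression status. A reader might infer that enforcing the 2 weeks costs at most 14 days; Step 3 shows that this fails for a child still tapering. And a reader might assume that few children are affected; no count is given.

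**Conclusion.** The inconsistency is real and lies in current text. For a post-transplant child with no GVHD history, the required time off systemic immunosuppression is 14 days under 1.4.2 and none under criterion 9, and no other section supplies it. The mismatch is certain. Which text reflects the sponsor's intent is less so, although the allowances for topical therapy and physiologic hydrocortisone read more naturally as exceptions to a general bar. Allowing steroid below 0.5 mg/kg/day may be deliberate, given the restart rule in 8.2.1, but it is not stated as an entry exception. The conclusion assumes that 1.4.2's shorter interval covers children without any GVHD. It claims nothing about the number affected, GVHD or CR/CRi rates, or the error rates of the stopping rule. It should be corrected because it decides who is dosed and when.

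**What to change.** Add to criterion 9 that every other post-transplant subject must have stopped all systemic immunosuppression, apart from topical therapy and physiologic hydrocortisone, at least 2 weeks before the first dose. Carry into 7.2 the study-chair discussion for prior Grade 3 or worse GVHD or therapeutic immunosuppression.

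If the sponsor does intend to admit children on prophylaxis, or on steroid below 0.5 mg/kg/day, state that exception in criterion 9 and correct 1.4.2 to match.

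Either route needs only an amendment to the wording. The clinical cost falls on the stricter one: a child still tapering waits the remaining taper plus 14 days, may outrun the 14-day screening window and may have to be rescreened. Section 1.4.2 already implies that wait.
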